6.4.2 MS relapse

The initial assessment, management and reporting of MS relapse is made by the Primary Treating Physician.

MS relapse definition: appearance of a new neurological abnormality or worsening of previously stable or improving pre-existing neurological abnormality, separated by at least 30 days from onset of a preceding clinical demyelinating event (McDonald et al 2001). The abnormality must have been present for at least 24 hours and occurred in the absence of fever (< 37.5°C) or known infection.

Diagnosing MS relapses during the study: a patient may report symptoms indicative of a relapse at a scheduled visit or at any other time. Patients will be instructed to immediately contact the Primary Treating Physician if he/she develops new or re-occurring or worsening neurological symptoms. At each scheduled visit, the patient will also be asked whether any such symptoms have occurred. If a patient reports new neurological symptoms or worsening of previous symptoms, an unscheduled visit is to be planned as soon as possible, ideally within 7 days. During this visit, the treating physician will first assess whether the new/worsening neurological abnormality is consistent with the definition of MS relapse above. If so, the standard neurological examination (for the EDSS score) should be performed by the Independent Evaluating Physician (EDSS rater). If there is any doubt in the opinion of the treating physician, the default must always be to refer the case to the Independent Evaluating Physician to perform an EDSS rating.

During the Extension Phase the EDSS assessment needs to be completed by a qualified EDSS rater. Blinding of EDSS ratings is not required during the Extension Phase since all patients will be treated with fingolimod. However, it is highly recommended that the EDSS rater used in the Core Phase continues to monitor the EDSS in the Extension Phase for consistency of readings. If a rater change is required then adjudication/discussion between "Core Phase Rater" and "Extension Phase Rater" should be done if there are differences between the last Core Phase evaluation and the first Extension Phase evaluation. Co-ratings are also recommended. Every effort should be made for the rater to remain the same throughout the study.

Confirmation of MS relapse: the definition of a confirmed MS relapse is one accompanied by a clinically relevant change in the EDSS performed by the Independent Evaluating Physician/EDSS rater for Core/Extension Phase respectively, i.e. an increase of at least 0.5 points on the EDSS score, or an increase of 1 point on two FSs or 2 points on one FS, excluding changes involving bowel/bladder or cerebral FS compared to the previous available rating (the last EDSS rating that did not occur during a relapse).

The main relapse-related analyses will be based on confirmed relapses. All relapses, confirmed and unconfirmed, will be recorded in the eCRF.

The severity of relapses will be calculated centrally according to criteria in [Table 6-4](#).

Table 6-4 Severity of MS relapse

Mild relapse	Moderate relapse	Severe relapse
EDSS increase of 0.5 point	EDSS increase of 1 or 2 points	Exceeding Moderate criteria
Or	or	or
1 point FS change in one to three systems	2-point FS change in one or two systems	Exceeding Moderate criteria
	or	or
	1-point change in four or more systems	Exceeding Moderate criteria
(Panitch et al 2002)		

6.4.3 (Kurtzke's) Expanded Disability Status Scale (EDSS)

EDSS will be determined, based on neurological examination, by the Independent Evaluating Physician during the Core Phase and by a certified EDSS rater during the Extension Phase at scheduled visits according to [Table 6-1](#), [Table 6-2](#) and [Table 6-3](#) and in case of a suspected MS relapse.

The EDSS is an ordinal scale used for assessing neurologic impairment in MS based on a neurological examination. It consists of scores in each of seven functional systems (FSs) that are then combined to determine the EDSS steps [ranging from 0 (normal) to 10 (death due to MS)]. The FSs are Visual, Brain Stem, Pyramidal, Cerebellar, Sensory, Bowel & Bladder, and Cerebral functions. EDSS is a widely used and accepted instrument to evaluate disability status at a given time and, longitudinally, to assess disability progression in clinical studies in MS.

The Independent Evaluating Physician/EDSS rater is a neurologist or otherwise qualified healthcare professional who has successfully completed the EDSS certification (at the highest level) within the past 12 months. During the Core Phase the Independent Evaluating Physician conducts the EDSS ratings and is otherwise not involved in the treatment of the patient. During the Extension Phase EDSS ratings may be done by a qualified healthcare professional that has successfully completed the EDSS certification.

EDSS assessments are to be performed at scheduled visits according to [Table 6-1](#), [Table 6-2](#) and [Table 6-3](#) and in case of an MS relapse.

6.4.5 Appropriateness of efficacy assessments

MS relapse, MRI and EDSS are standard efficacy assessments in MS and are used in both the adult and the pediatric populations. They serve to characterize the patient population included in this study as well as their disease activity and neurological status. [REDACTED]

6.5 Safety

Safety assessments will include:

- Physical examination (including skin)
- [REDACTED]
- Ophthalmologic examination including Optical Coherence Tomography (OCT)
- Pulmonary function tests (PFTs)
- Vital signs
- Laboratory evaluations
- Electrocardiogram (ECG)
- Columbia Suicide Severity Rating Scale (C-SSRS)

Medical history, including MS history and prior MS treatments will be assessed at Visit 1. Concomitant medications will be assessed at every visit following informed consent.

6.5.1 Physical examination

A physical examination will be performed according to [Table 6-1](#), [Table 6-2](#) and [Table 6-3](#) and will include an assessment of skin, head and neck, lymph nodes, breast, heart, lungs, abdomen, back and comments on general appearance. A complete neurological examination will be part of the initial physical examination at screening. Investigators should ask the patient/guardian if they have any new or changed skin lesions as part of each physical examination. If skin lesions (suspected to be precancerous or cancerous) are identified during the physical examination, the patients should be referred to a dermatologist.

A complete examination of the skin will be performed by a dermatologist or the study pediatrician according to [Table 6-1](#), [Table 6-2](#) and [Table 6-3](#).

Information for all physical examinations (including skin exams) must be included in the source documentation at the study site. Significant findings that are present prior to the start of study drug must be included in the Relevant Medical History/Current Medical Conditions screen on the patient's eCRF. Significant findings made after the start of study drug which meet the definition of an Adverse Event must be recorded on the Adverse Event eCRF.

6.5.2 Ophthalmologic examination

A complete ophthalmologic examination will be performed according to [Table 6-1](#) or [Table 6-3](#) by an ophthalmologist. At each scheduled visit the following assessments will be performed:

- Eye history (medical history at baseline, AEs during the study)
- Best corrected visual acuity measurements using a standard visual acuity chart with equal space between letters and between lines (results must be provided in Snellen equivalent or decimal score)
- Dilated ophthalmoscopy to examine the macula and optic disc (may include contact lens biomicroscopy)

- [REDACTED]

Optical coherence tomography (OCT) to measure central foveal thickness/center point thickness should be performed according to [Table 6-1](#) or [Table 6-3](#). An OCT should also be performed if there is suspicion of macular edema by dilated ophthalmoscopy at any visit. Further explorations, such as a fluorescein angiogram, to confirm/rule out macular edema should be performed at the discretion of the ophthalmologist

Patients with medical history of diabetes mellitus or uveitis or newly diagnosed uveitis at screening or during the study will require special evaluation and additional ophthalmic evaluation (see [Appendix 3](#)).

6.5.3 Vital signs

Vital signs will be recorded according to the schedule in [Table 6-1](#), [Table 6-2](#) and [Table 6-3](#). Vital signs will include height, weight, sitting pulse rate, sitting systolic and diastolic blood pressure, and oral temperature (degrees Celsius).

Heart rate (pulse)

Sitting radial pulse after 5 minutes of rest should be measured just prior to blood pressure measurement.

At least 6 hour monitoring in the clinic will be required on Day 1 (Visit 3) and Visit 15 after first dose of study drug in the Core and Extension Phase, respectively. This is also required in the event of an increase in fingolimod dose from 0.25 mg to 0.5 mg (see [Section 3.3](#)) and at any restart of study drug dosing after an interruption as specified in [Section 5.5.5](#). Details of the monitoring during treatment initiation, dose increase or study drug restart are provided in [Appendix 2](#).

In the Extension Phase, Visit 15 first dose monitoring must be done by the independent first dose monitoring team. All subsequent monitoring visits required per protocol for dose increases or study drug interruptions may be performed by the main study team since all patients will be treated with fingolimod in the Extension Phase and thus blinding is not required after the first dose of Extension Phase medication has been provided to a patient.

Blood pressure

Sitting blood pressure will be recorded according to the schedule in [Table 6-1](#), [Table 6-2](#) and [Table 6-3](#). Every effort should be made to have the same study personnel obtaining blood pressure readings for an individual patient at each visit at the same time of day with the same equipment. Using a calibrated standard sphygmomanometer with the appropriate cuff size, arterial blood pressure determinations will be made. With the arm supported at the level of the heart, systolic and diastolic blood pressure will be recorded. The cuff should not be deflated at a rate greater than 2 mmHg/sec.

At each visit after the patient has been resting (i.e., not active) for 5 minutes, systolic/diastolic blood pressure will be measured three times. For blood pressure measurements during first dose monitoring on Day 1, refer to [Appendix 2](#).

6.5.4 Laboratory evaluations

Routine blood and urine samples will be analyzed by the central laboratory. Details about collection, shipment of samples, reporting of results, laboratory normal ranges and alerting abnormal values will be provided in the study laboratory manual, supplied to the site before site initiation. With the exception of total and differential white blood cell count, which will be blinded to the sites (refer also to [Section 15.4](#)), the results of the analysis will be made available to each center by the central laboratory at the earliest 48 hours after receipt of the samples by the central laboratory.

Hematology

Complete blood cell count (CBC) analysis including red blood cell (RBC) count, total and differential white blood cell (WBC) count (basophils, eosinophils, lymphocytes, monocytes, neutrophils, WBC segments), platelet count, hemoglobin, hematocrit, MCV, MCH, MCHC and RBC morphology will be performed according to [Table 6-1](#), [Table 6-2](#) and [Table 6-3](#).

Additionally, phenotyping of T cells (naïve T cells, T central memory cells and T effector memory cells) and B cells using FACS flow cytometry will be performed according to [Table 6-1](#).

Blood chemistry

All laboratory samples are preferred to be collected at the same time of the day. Fasting status should be clearly identified on the laboratory requisition form accompanying the samples.

Blood chemistry is to be obtained according to [Table 6-1](#), [Table 6-2](#) and [Table 6-3](#) and will include sodium, potassium, chloride, calcium, magnesium, phosphate, blood urea nitrogen (BUN), uric acid, random glucose, albumin, alkaline phosphatase, creatinine, cystatin C, ALT, AST, GGT, amylase, total bilirubin, conjugated bilirubin, total cholesterol, triglycerides, HDL and LDL. Abnormal laboratory parameters should be repeated for accuracy. A blood sample for liver function tests only (ALT, AST, GGT, alkaline phosphatase, total bilirubin, conjugated bilirubin) will be obtained according to [Table 6-1](#). Serum pregnancy testing and home pregnancy testing will be performed according to [Table 6-1](#) and [Table 6-3](#).

To assist for patients with travel restrictions blood samples for liver panel assessments as described in [Table 6-1](#) (Visits at 6 weeks, 4 and 5 months) may be drawn by a local lab and the results report sent to the Investigator within 48 hours of obtaining the results.

If any significant findings are observed on these reports (See [Appendix 3 Section 15.2](#) guidelines), a confirmatory blood sample should be drawn by the site and sent to the central laboratory.

If no significant findings are observed then the results of the local laboratory values (including reference ranges) should be included in liver eCRF to document the values.

Blood samples for these visits may also be obtained by other methods as appropriate in a particular country or region and processed through the central laboratory (e.g., flying nurse, local phlebotomist etc.). Please follow [Appendix 3 Section 15.2](#) guidelines of the protocol for liver safety monitoring for these visits.

Blood Chemistry criteria that require permanent study drug discontinuation are listed in [Section 5.5.9](#).

Serology

[figure not shown]
Serology testing will be performed according to [Table 6-1](#) and will include the following (for documentation of serology status or for assessment of exclusion criteria): herpes simplex virus-1, herpes simplex virus-2, hepatitis A, B, C and E, human immunodeficiency virus (HIV), Epstein Barr virus (EBV), cytomegalo virus (CMV), AQP4 auto-antibodies and IFN- β neutralizing antibodies. Varicella-zoster virus, mumps, measles, rubella, diphtheria, tetanus, pertussis may also be tested in patients without evidence of immunity. Please refer to [Appendix 3 Guidance on Vaccinations](#) and [Guidance on monitoring of patients with infections](#) for guidelines based on screening serology status and for general monitoring guidelines.

Endocrinology

The following parameters will be tested for according to [Table 6-1](#), [Table 6-2](#) and [Table 6-3](#): Insulin-like growth factor 1 (IGF-1), insulin-like growth factor binding protein (IGFBP3); follicle stimulating hormone (3FSH) and stradiol (E-2) in girls, testosterone, LH (luteinizing hormone) in boys.

Urine measurements

Urinalysis will include urine protein, glucose, leucocytes, blood, specific gravity, pH, ketone, bilirubin and urobilinogen and will be obtained according to [Table 6-1](#), [Table 6-2](#) and [Table 6-3](#).

Assessment of Tanner stages should be performed per local practice, guided by a pediatrician or health care professional experienced with this assessment. The Tanner scale assesses physical development in children, adolescents and adults (Marshall and Tanner 1970). The scale defines the physical measurements of development based on external primary and secondary sex characteristics. Tanner staging (breast development in girls and testes size in boys) is important for accurate interpretation of bone age and endocrine laboratory results. Patients with a Tanner Stage < II are considered pre-pubertal.

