Dose-dependent reductions in forced expiratory volume over 1 second (FEV1) and diffusion lung capacity for carbon monoxide (DLCO) were observed in patients treated with fingolimod. In MS controlled trials, mean reduction from baseline in percentage of predicted FEV1 at Month 1 was 1.89% for fingolimod 0.5 mg and 0.16% for placebo. At Month 24, the reduction from baseline in the percent of predicted values for FEV1 was 2.65% for fingolimod 0.5 mg and 1.24% for placebo. For DLCO, the reductions from baseline in percent of predicted values at Month 24 were 3.29% for fingolimod 0.5 mg and 1.16% for placebo. The changes in FEV1 appear to be reversible after treatment discontinuation. There is insufficient information to determine the reversibility of the decrease of DLCO after drug discontinuation. Cough and dyspnea were the most frequently reported respiratory AEs in the fingolimod 1.25 mg and 0.5 mg groups, but without significant differences between fingolimod patients and placebo [cough 9.1% and 9.6% for fingolimod 1.25 mg and 0.5 mg respectively, placebo 10.4%; dyspnea 7.2% and 6.0% for fingolimod 1.25 mg and 0.5 mg respectively, placebo 6.2%]. Few patients with a history of asthma experienced changes in PFTs to less than 80% or 60% of baseline values at a single visit or 2 consecutive visits. Overall, there was no evidence that patients with a history of asthma were at increased risk of pulmonary function changes amongst the treatment groups.

A key pharmacodynamic effect of fingolimod is a dose-dependent reduction of peripheral lymphocyte count to 20 - 30% of baseline values. This is due to the reversible sequestration of lymphocytes in lymphoid tissues. The overall rate of infections (in study D2301 72% on fingolimod vs. 72% on placebo) and serious infections (in study D2301 1.6% on fingolimod vs. 1.9% on placebo) at the 0.5 mg/day dose, fingolimod was similar to placebo. However, lower respiratory tract infections, primarily bronchitis, were more common in fingolimod treated patients (in study D2301 8.0% on fingolimod vs. 3.6% on placebo for bronchitis and 0.5% on vs. 0.2% for pneumonia). There was no clear relationship between lymphocyte count and the incidence of infections on fingolimod treatment. In the clinical trial program, there were 3 cases of disseminated herpes infection with organ involvement other than skin in patients treated with fingolimod 1.25 mg. Two fatal cases: herpes simplex encephalitis in a

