Patients who prematurely discontinue study drug during the Core Phase should be encouraged to remain in the study. Patients who prematurely withdraw (PPW – Premature Patient Withdrawal) from the study for any reason should be scheduled for a final Visit 14 (EOS-CP) assessment at the time of discontinuation from study drug as outlined in [Table 6-1](#)). A follow-up visit should then be scheduled three months after the last dose of the study drug. If the patient is unable to return to the site for the Visit 14 / EOS-CP assessments, every effort should be made to contact the patient by telephone for safety evaluations during the 3 months

following the last dose of study drug, including a final contact at the 90-day point (3-month follow up).

Patients who prematurely discontinue study drug (SDD) during the Core Phase, and remain in the study will follow an abbreviated schedule of assessments (see [Table 6-2](#)). At the time of SDD, patients must complete the Visit 14 / EOS-CP assessments (as end of treatment assessments), followed by a 3-month follow-up visit prior to continuing in the abbreviated schedule of assessments. If a patient who is being followed in the abbreviated schedule of assessments prematurely withdraws from the study, the patient should be scheduled for a final visit (EOS-CP according to [Table 6-2](#)) at the time of study discontinuation.

Patients who have completed the Core Phase, as per [Table 6-1](#) or [Table 6-2](#), may be eligible to enter the long-term extension study ([Table 6-3](#)). Patients who complete the Core Phase on study drug, but choose not to enter the Extension Phase should return for a 3-month follow-up visit.

Patients who prematurely discontinue study drug (SDD) during the Extension Phase, may remain in the study and be followed at yearly visits (see [Table 6-2](#)). At the time of SDD, patients must complete the Visit 30 assessments (as end of treatment assessments), followed by a 3-month follow-up visit.

Table 6-2 Core Phase: Abbreviated schedule of assessments for patients with SDD

Phase	Double-blind Treatment Phase						
Visit No. ¹	8	9	10	11	12	13	14/ EOS-CP
Study month	6	9	12	15	18	21	24
Physical exam	X		X		X		X
Skin exam							X
[REDACTED]							
Pulmonary Function Tests	X		X		X		X
MS relapses	X	X	X	X	X	X	X
MS treatment/Concomitant medications/Steroids	X	X	X	X	X	X	X
EDSS	X	X	X	X	X	X	X
MRI	X		X		X		X
[REDACTED]							
Vital signs	X	X	X	X	X	X	X
Hematology/Blood chemistry	X		X		X		X
[REDACTED]							

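### Protocol 6.5.4 and 15.4 do not withhold T- and B-cell phenotyping from sites, so a result that could reveal the arm may reach the physician who screens relapses

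*Protocol*

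**What the plan says.** **Release rule.** Protocol Section 6.5.4 gives one rule for central laboratory results. It opens "With the exception of total and differential white blood cell count, which will be blinded to the sites" and continues that "the results of the analysis will be made available to each center by the central laboratory at the earliest 48 hours" after the samples arrive. Section 15.4 blinds total white cell, neutrophil and lymphocyte counts from investigator and sponsor, and tells the site only of notable abnormalities. It does not mention phenotyping.

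**Tests outside the exception.** Under Hematology, Section 6.5.4 adds phenotyping of naive and central memory T cells, "T effector memory cells) and B cells using FACS flow cytometry will be performed" according to Table 6-1. Its Serology list includes "AQP4 auto-antibodies and IFN- β neutralizing antibodies".

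**Drug effect.** Section 1.1 describes a marked fall in both B and T lymphocytes in the circulation, and "a dose-dependent reduction of peripheral lymphocyte count to 20 - 30% of baseline values".

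**Who must be blinded.** Section 5.4 keeps patients, treating physician, site personnel, rater and nearly all sponsor staff blinded until database lock. The specific measures listed there protect the EDSS rater, including the bar on seeing laboratory data.

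**Who screens relapses.** Under Section 6.4.2, when a patient reports symptoms, "the treating physician will first assess whether the new/worsening neurological abnormality is consistent with the definition of MS relapse above". Only then does the independent rater perform the EDSS, and confirmation depends on that rating.

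**The concern.** The exception for white cell counts has an evident purpose: fingolimod's effect on lymphocytes would show the arm. Phenotyping measures T and B cells, the populations that the protocol says the drug lowers. A rule that hides the lymphocyte count but leaves phenotyping uncovered does not fully serve that purpose.

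At stake is the first step in counting the primary endpoint. An event that the treating physician does not recognise and refer never reaches the rater and cannot become a confirmed relapse. If that physician could infer the arm, the threshold for referral could differ between arms, and the rater's own blinding would not correct it. The protocol cares about this physician's blind elsewhere: Section 5.5.13 has the First-dose Administrator keep vital signs from the treating physician and nurse unless medically warranted. The Amendment 1 summary also records that independent relapse adjudication was dropped because the design became double-blind, so the blind now carries that weight.

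**Working it through.** The point turns on the text, so the first check sets the rules beside the tests.

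| Result | Covered by the 6.5.4 exception? | Covered by 15.4? |
|---|---|---|
| Total white cells | Yes | Yes |
| Differential, including neutrophils and lymphocytes | Yes | Neutrophils and lymphocytes |
| T-cell subsets and B cells by flow cytometry | Not named | Not named |
| Interferon neutralising antibodies | Not named | Not named |

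**Step 1: does another readable passage withhold phenotyping?** None does. Section 5.4 imposes blinding in general but names no laboratory test. SAP Table 3-1, footnote 1, mentions information that belongs to a blinded database but does not list its contents.

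**Step 2: could the result carry the signal?** Section 1.1 says both T and B cells fall markedly. The 20–30% figure is for the total peripheral lymphocyte count; no figure is given for any subset. The direction is documented, but the size for the reported quantity is not.

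**Step 3: can it reach the endpoint?** The chain is report to site, treating physician, decision to refer, EDSS rating, confirmed relapse. Sections 6.4.2 and 5.4 establish every link except the first, which depends on whether and when phenotyping is reported.

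**Step 4: neutralising antibodies.** Protocol 9.5.3 summarises them at the end-of-Core-Phase visit, too late to affect screening in patients who complete on drug. Early discontinuers differ. Protocol Section 6 says "At the time of SDD, patients must complete the Visit 14 / EOS-CP assessments (as end of treatment assessments"; they may then stay in follow-up, and Section 9.4.3 counts relapses off drug. But Section 5.5.7 allows interferon up to the day before Day 1, so a positive result is informative mainly in patients without earlier interferon.

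**Scale only.** The plan's design figures (Protocol 9.6) are 95 per arm, T = 2 years, rates 0.18 and 0.36, and dispersion 0.82. Equation 2 of Appendix 5 gives:

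- I = 95 / [1/(0.18×2) + 1/(0.36×2) + 2×0.82] = 95 / (2.778 + 1.389 + 1.640) = 16.36, as stated.
- SE of the log rate ratio = 1/√16.36 = 0.247.
- Power = Φ(0.693/0.247 − 1.96) = 80.06%, against the stated 80%.

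Now assume no true effect, and that fingolimod relapses are referred at a ratio r relative to interferon across the whole arm, with the SE unchanged. The chance of a significant result favouring fingolimod is Φ(−1.96 − ln r / 0.247):

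| r (assumed) | Chance |
|---|---|
| 1.00 | 2.5% |
| 0.95 | 4.0% |
| 0.90 | 6.3% |
| 0.80 | 14.5% |

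No value of r comes from the documents. The table shows how sensitive the test is to differential referral; it does not predict any.

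**The case against.** The strongest reply is that nothing says phenotyping goes to sites. The release paragraph begins "Routine blood and urine samples will be analyzed by the central laboratory", phenotyping is introduced separately as an addition, and reporting details are left to a laboratory manual that is not among the documents. Section 5.4 requires the site to stay blinded, and the SAP's blinded database shows that a separate channel exists. If the reports were absolute T and B counts, they would largely disclose the lymphocyte count that 15.4 already hides, so its intent arguably covers them. This stands against reading the text as proof that phenotyping is released. It does not close the gap, because the only written exception omits the test.

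Timing is also unknown. The body of Table 6-1 is not in the text available. If the only post-baseline sample were at the end of the Core Phase, the mechanism would fail for patients who complete on drug. That stands.

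There are real safeguards. Section 6.4.2 makes referral the default whenever the treating physician is in doubt, the rater is blinded, and unconfirmed relapses are recorded and analysed. These limit the effect. But doubt is judged by the same physician, and an event never recognised enters no analysis. SAP deviations O02 and O02A remove blinding failures from the per-protocol set only, not from the primary analysis.

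A reader might go on to infer that one before-and-after pair identifies the arm in nearly every patient, or that the rate ratio shifts by a given amount. The documents support neither: they give no subset effect, within-patient variability, report format or referral loss. Nor should arm-related drug discontinuation be counted as a direct loss of endpoint events, because relapses count on or off drug.

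**Conclusion.** The gap in wording is real and worth correcting. Read literally, 6.5.4 and 15.4 do not withhold a test that could carry the lymphocyte signal the exception is meant to hide, and the person it could unblind is the first gate to a confirmed relapse.

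The conclusion is conditional. It assumes that phenotyping is reported to sites during the Core Phase, at a post-baseline visit early enough to matter, and in a form that shows the fall. The laboratory manual may already prevent this, in which case the change only records existing practice. The size of any bias cannot be estimated from the documents.

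A reader might treat the antibody results as an equal route to unblinding. They are not: the route is confined to patients who stop drug early and remain in follow-up, and mainly to those without earlier interferon. It justifies a precaution only.

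**What to change.** Extend the exception in Protocol 6.5.4 and the blinding sentence in 15.4 so that lymphocyte phenotyping results are withheld from site staff and the blinded sponsor team until Core Phase database lock. Route them to the blinded database, and make the laboratory manual agree. Leave the existing white cell, neutrophil and lymphocyte alerts unchanged. As a secondary precaution, treat post-baseline interferon neutralising-antibody results in the same way; screening results are not affected.

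The cost is one sentence in each section and a reporting setting at the central laboratory. The downside is that investigators do not see these results during the Core Phase. No readable patient-care rule uses phenotyping or on-study antibody results, and Appendix 1 sets no notable values for them. Some text is redacted, so the sponsor should confirm this before making the change.
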